4.3.3 Treatment of Nivolumab-related infusion reactions

Since nivolumab contains only human immunoglobulin protein sequences, it is unlikely to be immunogenic and induce infusion or hypersensitivity reactions. However, if such a reaction were to occur, it might manifest with fever, chills, rigors, headache, rash, pruritus, arthralgias, hypotension, hypertension, bronchospasm, or other allergic-like reactions.

Treatment recommendations are provided below and may be modified based on local treatment standards and guidelines, as appropriate:

Table 4-2: Nivolumab Infusion Reactions

NCI CTCAE Grade	Treatment	Premedication at subsequent dosing
Grade 1 Mild reaction; infusion interruption not indicated; intervention not indicated	Remain at bedside and monitor subject until recovery from symptoms.	The following prophylactic pre-medications are recommended for future infusions: 
 ● Diphenhydramine 50 mg (or equivalent) and/or ● Acetaminophen 325 to 1000 mg at least 30

NU Study Number: NU 16L04
Other Study Number: CA 209-801

Table 4-2: Nivolumab Infusion Reactions		
NCI CTCAE Grade	Treatment	Premedication at subsequent dosing
Grade 2 Moderate reaction requires therapy or infusion interruption but responds promptly to symptomatic treatment [eg, antihistamines, non-steroidal anti- inflammatory drugs, narcotics, corticosteroids, bronchodilators, IV fluids]; prophylactic medications indicated for < 24 hours	
Stop the nivolumab infusion, begin an IV infusion of normal saline, and treat the subject with diphenhydramine 50 mg IV (or equivalent) and/or acetaminophen 325 to 1000 mg;
 
Remain at bedside and monitor subject until resolution of symptoms.
 
Corticosteroid and/or bronchodilator therapy may also be administered as appropriate. If the infusion is interrupted, then restart the infusion at 50% of the original infusion rate when symptoms resolve; if no further complications ensue after 30 minutes, the rate may be increased to 100% of the original infusion rate.
 
Monitor subject closely. If symptoms recur, then no further nivolumab will be administered at that visit.
	
minutes before additional nivolumab administrations
 
For future infusions, the following prophylactic pre-medications are recommended:
 
 • Diphenhydramine 50 mg (or equivalent) and/or • Acetaminophen 325 to 1000 mg should be administered at least 30 minutes before nivolumab infusions. If necessary, corticosteroids (up to 25 mg of SoluCortef or equivalent) may be used.
Grades 3 or 4 Severe reaction, Grade 3: prolonged [ie, not rapidly responsive to symptomatic medication and/or brief interruption of infusion]; recurrence of symptoms following initial improvement; hospitalization indicated for other clinical sequelae [eg, renal impairment, pulmonary infiltrates]. Grade 4: Life-threatening; pressor or ventilatory support indicated	
Immediately discontinue infusion of nivolumab infusion. Begin an IV infusion of normal saline and treat the subject as follows:
 
Recommend bronchodilators, epinephrine 0.2 to 1 mg of a 1:1000 solution for subcutaneous administration or 0.1 to 0.25 mg of a 1:10,000 solution injected slowly for IV administration, and/or diphenhydramine 50 mg IV with methylprednisolone 100 mg IV (or equivalent), as needed.
 
Subject should be monitored until the Investigator is comfortable that the symptoms will not recur. Nivolumab will be permanently discontinued. Investigators should follow their institutional guidelines for the treatment of anaphylaxis.
 
Remain at bedside and monitor
	No subsequent dosing

NU Study Number: NU 16L04
Other Study Number: CA 209-801

Table 4-2: Nivolumab Infusion Reactions		
NCI CTCAE Grade	Treatment	Premedication at subsequent dosing
	
subject until recovery of the symptoms
 
In case of late-occurring hypersensitivity symptoms (eg, appearance of a localized or generalized pruritus within 1 week after treatment), symptomatic treatment may be given (eg, oral antihistamine or corticosteroids)
	

Immunotherapy agents such as nivolumab are associated with AEs that can differ in severity and duration compared to other therapeutic classes of medications. Early recognition and management of AEs associated with nivolumab can mitigate severe toxicity. Corticosteroids are the primary therapy for drug-related AEs. Management algorithms have been developed to assist investigators in assessing and managing nivolumab associated AEs, which can be found in Appendix D of this protocol. The guidance provided in these algorithms should not replace the Investigator's medical judgment.

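### Table 4-2 gives symptoms that recur after a restarted Grade 2 infusion a visit-limited stop in one row and, through its Grade 3 criterion, a permanent stop in the next

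*Combined protocol and SAP*

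**What the plan says.** Section 4.2.1 refers acute infusion reactions to Section 4.3.3, whose Table 4-2 sets the management by grade.

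- **Grade 2 row, treatment.** The infusion is stopped and the patient treated. If it was interrupted, staff are to "restart the infusion at 50% of the original infusion rate when symptoms resolve". The row then deals with recurrence itself: "If symptoms recur, then no further nivolumab will be administered at that visit".
- **Grade 2 row, premedication column.** "For future infusions, the following prophylactic pre-medications are recommended". The entry makes no exception for a patient whose symptoms recurred.
- **Grades 3 or 4 row, definition.** One of the listed Grade 3 features is "recurrence of symptoms following initial improvement".
- **Grades 3 or 4 row, action.** "Nivolumab will be permanently discontinued", and the last column reads "No subsequent dosing".
- **Section 4.3.2.** A drug-related Grade 3 infusion reaction is on the list for permanent discontinuation, regardless of how long it lasts. When nivolumab stops for toxicity the patient leaves study treatment, because metformin alone is not allowed on study.

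The table is introduced as recommendations that local standards may modify. Section 4.3.2 carries no such allowance.

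**The concern.** The Grade 2 row foresees recurrence and gives an instruction for it that is limited to one visit. The row below describes what reads as the same clinical course and ends nivolumab for good. The Grade 2 row points neither to that row nor to Section 4.3.2, and does not say that a recurrence changes the grade.

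What is at stake is whether one patient gets nivolumab again after a recurrent infusion reaction. Section 4.3.3 lists hypotension and bronchospasm among the possible manifestations. The opposite error also has a cost: if the trial meant to allow a further attempt, a strict reader would take the patient off all study treatment unnecessarily.

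**Working it through.** The plan gives no figure to reproduce. The check is to follow one patient through the rules and then bound how many patients could be affected.

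**One patient through the table**

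1. A Grade 2 reaction occurs and the infusion is stopped.
2. Symptoms resolve. Only then may the infusion restart, at half rate ("restart the infusion at 50% of the original infusion rate when symptoms resolve").
3. Symptoms return. Because step 2 required resolution, this is necessarily a return after improvement.
4. The rules that now apply are:

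| Rule | Does it describe this event? | Instruction on nivolumab |
|---|---|---|
| Table 4-2, Grade 2 row | Yes, by name | None for the rest of that visit; silent on a permanent stop; premedication advised for later infusions |
| Table 4-2, Grades 3 or 4 row | Yes, by the criterion "recurrence of symptoms following initial improvement" | Permanent stop, no later doses |
| Section 4.3.2 | Only once the event is graded 3 | Permanent stop, any duration |

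The first rule differs from the other two on what happens at the next visit.

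**Who can reach the sentence**

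Only a Grade 2 reaction that was interrupted and restarted. Grade 1 is defined as "Mild reaction; infusion interruption not indicated; intervention not indicated", so nothing is restarted. An initial Grade 3 or 4 reaction carries "Immediately discontinue infusion of nivolumab infusion" and a permanent stop.

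**Upper bound on numbers**

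- Section 8.1.10 lists infusion-related reactions among events expected in less than 10% of patients. Target enrolment is 51.
- Any reaction: below 51 × 0.10 = 5.1 patients.
- At the stated minimum enrolment of 21: below 21 × 0.10 = 2.1 patients.
- Patients with a recurrence after restart = (patients with any reaction) × (share that are restarted Grade 2) × (share of those that recur). The documents give neither share, so the count can only be said to be some fraction of about 5.

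**Difference for one patient**

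Cycles 1 to 4 carry 2 doses of 240 mg each: 4 × 2 = 8. If the recurrence is at the first infusion and treatment would otherwise run through Cycle 4, the two readings differ by up to 8 − 1 = 7 further 240 mg doses against none, before counting any 480 mg doses from Cycle 5.

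**The case against.** The best reply is that both instructions can be obeyed. The Grade 2 sentence says what to do in the infusion chair and is silent about the next visit. Section 4.2.1 sends staff to the whole of 4.3.3, not to one row. A reader who sees that the event now meets the Grade 3 criterion goes to the next row and to 4.3.2, and stops. This stands to the extent that the protocol does contain the means to reach the stricter answer. It does not remove the problem, because the Grade 2 row names the event, supplies its own visit-limited action beside advice for later infusions, and never tells the reader to regrade.

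Other parts of the reply also have force:

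- The Grade 3 cell opens by describing a severe reaction, so whether a brief, mild recurrence belongs there is open to clinical reading. That is a reason to state the intent.
- Section 4.3.2 does not mention recurrence. It applies only through the table's own grading.
- The premedication column serves all Grade 2 reactions, so it does not show that rechallenge after recurrence was intended.
- Section 4.3.1 delays nivolumab for most drug-related non-skin events of Grade 2 or above until they recover to Grade 1 or baseline, and 4.2.1 keeps 240 mg doses at least 12 days apart. Re-exposure would generally follow recovery, but neither rule makes the stop permanent.

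A reader might infer that the protocol orders re-dosing, or that nothing in it settles the matter. The text supports neither: the Grade 2 row is silent on the next visit, and the Grade 3 row with 4.3.2 leads to a stop.

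**Conclusion.** Wrong as written: an internally inconsistent safety rule, of minor severity. A recurrence after a restarted Grade 2 infusion meets a visit-limited stop in one row and the Grade 3 criterion, with its permanent stop, in the next. Section 4.3.2 adds its requirement only through that grading. A careful reader of the whole table would stop; the Grade 2 wording could still lead to re-exposure of a patient who should not be dosed again.

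The number affected is small. The bound of about 5 of 51 covers any infusion reaction and assumes that the rate in 8.1.10, from patients given nivolumab alone, carries over to the combination. Recurrences after restart are a subset of unknown size. A chance of seeing at least one could be computed only by assuming the two missing shares, and plausible choices give so wide a range that the result says little. The inconsistency does not depend on it.

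A reader might also infer an effect on adverse event grading or on the response analysis. Neither is claimed. Section 7.2.2 grades all events by CTCAE v4.03 independently of this table, and the point here concerns only whether nivolumab is given again.

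**What to change.** In the Grade 2 row of Table 4-2, replace the recurrence sentence with: *If symptoms recur after restart, stop the infusion and manage as Grade 3: permanently discontinue nivolumab per 4.3.2.* If the medical lead does intend to allow a further attempt after recurrence, that exception should be written into both the Grade 3 row and 4.3.2 instead.

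The cost is one sentence in the next amendment, with no extra patients, visits or procedures. The downside is that a few patients with a mild recurrence lose later nivolumab and come off all study treatment. The Grade 3 row and 4.3.2 already require that outcome, so the edit makes the existing rule visible where staff will look for it.

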4.3.4 Metformin

The most common adverse reactions to metformin are diarrhea, nausea/vomiting, flatulence, indigestion, and headaches. These side effects occur most commonly upon initiation of therapy and are short lived. These effects are mitigated by dose escalation regimens that are used in this trial. Dose reduction or discontinuation will be applied in patients with persistent gastrointestinal symptoms related to metformin. A rare but serious side effect of metformin is lactic acidosis, which is most common in patients with renal insufficiency and congestive heart failure. Lactic acidosis can be evaluated by checking a patient's renal function in addition to their serum lactic levels. Any clinical or laboratory indication of metabolic acidosis will lead to immediate discontinuation of metformin.

For commonly observed gastrointestinal AEs of metformin such as nausea, vomiting and diarrhea the dose should be withheld. Metformin should be held until the AE resolves to \leq Grade 1 or baseline and restarted at a lower dose level as per Table 4-3. Metformin can be held for a maximum of 28 days. Patients who permanently discontinue metformin for toxicity must come off study treatment – they may not receive nivolumab monotherapy on-study.

Metformin-induced side effects as determined by the study investigator should be managed as listed below in tables 4-3 and 4-4.

Table 4-3: Metformin-related toxicity dose reductions	
CTCAE Grade	Metformin Dosing
0-2	No change from original starting dose
3 (1 st occurrence)	Hold until resolved to \leq grade 1 or baseline, then reduce to lower dose
3 (2 nd occurrence)	Hold until resolved to \leq grade 1 or baseline, then reduce to lower dose
3 (3 rd occurrence) or 4	Discontinue treatment

Table 4-4: Dose reduction of Metformin for toxicity	
Current dose	Reduced dose
2000 mg	1500 mg
1500 mg	1000 mg
1000 mg	500 mg
500 mg	Discontinue*

Note: For the purpose of imaging with CT scan with IV contrast, metformin can be held according to the institution's CT scan protocol.

*Patients will discontinue all study treatment

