8.2.10 Side effects

Frequent (>10%)

Diarrhea, nausea, and flatulence. These side effects typically subside after continued use of the medicine.

Less Frequent (≤ 10%)

Asthenia, Indigestion, abdominal discomfort and Headache

Rare and serious

A rare severe side effect is lactic acidosis (1 in 33,000 patients). The symptoms of lactic acidosis included feeling very weak, tired, or uncomfortable, unusual muscle pain, trouble breathing, unusual or unexpected stomach discomfort, feeling cold, feeling dizzy or lightheaded, and suddenly developing a slow or irregular heartbeat.

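### Section 4.3.4 gives two incompatible instructions for metformin-related gastrointestinal adverse events, most clearly at grade 2

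*Combined protocol and SAP*

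**What the plan says.** Section 4.3.4 (Metformin) covers gastrointestinal events in three places.

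- **Prose rule.** "For commonly observed gastrointestinal AEs of metformin such as nausea, vomiting and diarrhea the dose should be withheld". Metformin stays on hold until the event reaches "Grade 1 or baseline and restarted at a lower dose level as per Table 4-3". A hold may last at most 28 days. No CTCAE grade is given as the trigger for the hold.
- **Table rule.** The next paragraph states: "Metformin-induced side effects as determined by the study investigator should be managed as listed below in tables 4-3 and 4-4". Table 4-3 then gives, for grades 0 to 2, "No change from original starting dose". For a first or second grade 3 event it says to hold until "grade 1 or baseline, then reduce to lower dose". For a third grade 3 event or any grade 4 event it says "Discontinue treatment". No exception is made for gastrointestinal events.
- **Persistence rule.** A sentence earlier in the section provides for dose reduction or discontinuation when metformin-related gastrointestinal symptoms persist, again without a grade.

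Table 4-4 sets the reduction steps: 2,000 to 1,500 to 1,000 to 500 mg, and then discontinuation of all study treatment. The prose says the same of stopping the drug: "Patients who permanently discontinue metformin for toxicity must come off study treatment". Section 4.1 gives a starting dose of 1,000 mg and a target of 2,000 mg.

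**The concern.** A site managing a grade 2 nausea, vomiting or diarrhea event attributed to metformin can follow the section in two ways. One is to hold the drug and restart lower; the other is to leave the dose alone. Both have direct support in the current text.

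Metformin is the component this trial adds to nivolumab, and permanent discontinuation of metformin for toxicity ends both drugs. The rule a site picks can therefore change how much metformin a patient receives and, after repeated events, whether the patient remains on the combination. Section 4.3.4 itself describes gastrointestinal effects as among the most common reactions to metformin, so this part of the section is likely to be consulted. Two investigators could treat identical events differently and both be adhering to the protocol.

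**Working it through.** The plan states no figure on this point, so there is none to reproduce. The check compares the prose with Table 4-3 grade by grade, then counts steps in Table 4-4.

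**Step 1. Comparison for a metformin-related gastrointestinal event (Section 4.3.4)**

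| Event | Prose, read literally | Table 4-3 | Result |
|---|---|---|---|
| Grade 1 | Hold, restart lower; release condition already met | No change | Conflict on literal wording only |
| Grade 2 | Hold, restart lower | No change | Direct conflict |
| Grade 3, first or second | Hold, restart lower | Hold, then reduce | Agree |
| Grade 3, third | Hold, restart lower | Discontinue | Conflict on literal wording |
| Grade 4 | Hold, restart lower | Discontinue | Conflict on literal wording |

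The grade 2 reading of the prose is an inference. No trigger is stated, but a hold that ends at grade 1 fits one that begins at grade 2.

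**Step 2. Does the cross-reference settle it?** The pointer to Table 4-3 is attached to the restart at a lower dose. It is not attached to the sentence that orders the hold, so it does not supply a trigger grade for the hold. The pointer is also imprecise, because the lower dose levels are in Table 4-4.

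**Step 3. Consequence on the Table 4-4 ladder.** Inputs are the four dose levels in Table 4-4. The assumptions are that every grade 2 event follows the prose, that each resolves within the permitted hold, and that the dose is not raised again after a reduction.

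- From 2,000 mg: event 1 gives 1,500, event 2 gives 1,000, event 3 gives 500, event 4 gives discontinuation. All study treatment ends at the 4th event.
- From 1,500 mg: 1,000, 500, discontinuation. It ends at the 3rd event.
- From 1,000 mg: 500, discontinuation. It ends at the 2nd event.
- Under Table 4-3, any number of grade 2 events gives 0 holds and 0 reductions.

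**Step 4. Reference dose.** The grade 0 to 2 row is tied to the original starting dose. By Section 4.1 that is 1,000 mg, while a fully escalated patient takes 2,000 mg. The row does not say which dose is meant for a patient already escalated, or whether escalation continues for a patient still below target.

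**The case against.** The strongest defence is that Table 4-3 governs. The prose points to it, the following sentence sends metformin side effects generally to the tables, and the prose action nearly repeats the grade 3 row. On that view the prose merely summarises that row. This is a possible reading, but the text does not establish it: the pointer qualifies the restart, and nothing limits the hold to grade 3. A reader at grade 2 is still left with two instructions.

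Several limits on the point do stand.

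- Prose and table do not oppose each other throughout. They agree for the first two grade 3 events, and the grade 1 difference is only literal.
- These are the most common reactions to metformin, not of the trial regimen. Section 8.1.10 lists higher frequencies for nivolumab effects, such as fatigue at 50%.
- The starting-dose wording is loose and secondary. The natural reading is to leave the current dose alone, and Table 4-4 works from the current dose.
- Section 4.3.4 describes these effects as occurring mostly at initiation and as short lived, and Section 4.1 makes escalation depend on tolerance. That gives some latitude early on but does not settle later grade 2 events.

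Two stronger readings are tempting. First, a reader might multiply the frequency band in Section 8.2.10, which places "Diarrhea, nausea, and flatulence" above 10%, by the enrolment target to count affected patients. That band carries no grade, so it does not count patients for whom the two rules differ. Second, a reader might infer that the conflict alters the denominator of the response rate, because Section 6.3 makes patients removed from the study for adverse drug reactions inevaluable. This is possible but not shown. Section 4.7 continues imaging for patients who stop for toxicity without progression and counts a later response. Section 4.8 separates leaving treatment from leaving the study, and Section 10.3 analyses evaluable patients whatever their drug exposure.

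**Conclusion.** The inconsistency is real and lies in the current text of one section. It is a direct conflict at grade 2, on the inference that the ungraded hold covers grade 2. There is a further literal mismatch at grade 4 and at the third grade 3 event, and a loosely worded reference dose.

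For an individual patient the difference runs from no dose action at all to the end of all study treatment, at the second grade 2 event from 1,000 mg or the fourth from 2,000 mg, under the assumptions in the working. At trial level the size cannot be computed, because the documents give no grade 2 gastrointestinal event rate for this regimen. An effect on the evaluable set is not claimed. The point merits correction because it concerns a stated treatment rule that bears on metformin exposure and continuation. It does not by itself call the design or the primary analysis into question.

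**What to change.** Reconcile the Section 4.3.4 prose with Tables 4-3 and 4-4 so that each grade and occurrence of a metformin-related gastrointestinal event has exactly one action. In the same edit:

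- say how the separate sentence on persistent symptoms relates to the graded table;
- direct the reader to Table 4-4 for the reduced dose levels;
- state which dose the grade 0 to 2 row refers to, including for a patient still escalating.

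The clinical team decides what the actions should be; this review takes no position on which instruction is right. The cost is a wording amendment with notice to the study team. No change to the sample size or the analysis is needed.

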4.4 Continuation of Investigational Therapy after Progression

In the event of an initial assessment of progressive disease (PD, based on RECIST Version 1.1), a subject may continue to receive the assigned study treatment as long as the criteria listed below are met and eligibility to continue is documented in the medical record at the time the decision is made to continue treatment.

1. No confirmed PD: a subsequent scan obtained at least 4 weeks from prior scan is not suggestive of PD by RECIST 1.1 (see section 6.4.2), and the patient does not have clinical decline.
 NOTE: If PD is confirmed but the patient continues to have clinical benefit (e.g. improvement of symptoms and is tolerating treatment), the patient can continue treatment beyond PD per clinician's discretion.
2. Does not meet any of the other investigational product discontinuation criteria (Section 4.4.2)
3. Clinical symptoms or signs indicating significant PD such as the benefit-risk ratio of continuing therapy is no longer justified.
4. No decline in ECOG performance status.
5. No threat to vital organs/critical anatomical sites (eg, spinal cord compression) requiring urgent alternative medical intervention, and continuation of study therapy would prevent institution of such intervention.

If the lesions included in the tumor burden subsequently regress to the extent that the criteria for PD are no longer met, then treatment may continue according to the treatment schedule.

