Treatment Plan	
Patients will start metformin (Glucophage XR) at 1,000mg by mouth once daily during a 7-day induction period prior to starting nivolumab Cycle 1 Day 1 (1 cycle = 28 days). The dose will be increased by 500mg every 7 days (C1D1 and C1D8) until reaching the target dose of 2000mg. Nivolumab will be administered at a fixed dose of 240 mg IV every 14 days during Cycle 1-4 (Day 1 & 15) and 480mg IV every 28 days starting with Cycle 5 Day 1. Treatment will continue until disease progression confirmed by RECIST criteria v1.1, intolerable toxicity or withdrawal of consent. Imaging by CT or MRI will be scheduled every 2 cycles (8 weeks).

NU Study Number: NU 16L04
Other Study Number: CA 209-801

Statistical Methodology	
Accounting for invaluable patients and dropouts, up to 51 patients (Arm A=24, Arm B=25) will be entered into the trial based on optimal Simon two stage design as below.
 
Arm A: In the first stage, 9 patients will be entered. If no patients show a response, then the trial will be terminated due to inactivity of the treatment. If 1 or more of 9 show a response, then an additional 15 patients will be added. If 2 or fewer of 24 show a response, then the trial will conclude that the response rate could be as low as 5%. If 3 or more respond, then the trial will conclude that the response rate is at least 20%. This design has a 20% chance of falsely concluding the rate is 5% (false negative Type II error rate = 20%, or power = 80%), and a 10% chance of falsely concluding that the rate is 20% (false positive Type I error rate = 10%). There is a 63% probability of early termination of the trial when the true response rate is 5%.
 
Arm B: In the first stage, 12 patients will be entered. If 2 or fewer patients show a response, then the trial will be terminated due to inactivity of the treatment. If 3 or more of 12 show a response, then an additional 13 patients will be added. If 7 or fewer of 25 show a response, then the trial will conclude that the response rate could be as low as 20%. If 8 or more respond, then the trial will conclude that the response rate is at least 40%. This design has a 20% chance of falsely concluding the rate is 20% (false negative Type II error rate = 20%, or power = 80%), and a 10% chance of falsely concluding that the rate is 40% (false positive Type I error rate = 10%). There is a 56% probability of early termination of the trial when the true response rate is 5%.

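### Section 4.4 criterion 3 omits the negation the other four criteria carry, so the rule for treating after first progression inverts its benefit-risk condition

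*Combined protocol and SAP*

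**What the plan says.** Section 4.4 covers what happens after an initial RECIST 1.1 progression. The patient may continue "as long as the criteria listed below are met and eligibility to continue is documented" in the medical record. Five numbered criteria follow:

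- Criterion 1 asks for no confirmed PD, meaning that "a subsequent scan obtained at least 4 weeks from prior scan is not suggestive of PD by RECIST 1.1 (see section 6.4.2"), together with no clinical decline. A note allows the clinician to continue after confirmed PD if the patient is still benefiting.
- Criterion 2: "Does not meet any of the other investigational product discontinuation criteria (Section 4.4.2").
- Criterion 3: "Clinical symptoms or signs indicating significant PD such as the benefit-risk ratio of continuing therapy is no longer justified".
- Criterion 4: "No decline in ECOG performance status".
- Criterion 5: "No threat to vital organs/critical anatomical sites (eg, spinal cord compression) requiring urgent alternative medical intervention", where continuing would prevent that intervention.

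The section closes by saying that if lesions regress so far that "the criteria for PD are no longer met, then treatment may continue according to the treatment schedule". The Treatment Plan in the Study Summary says: "Treatment will continue until disease progression confirmed by RECIST criteria v1.1, intolerable toxicity or withdrawal of consent". Section 4.6 lists progression as a reason to stop unless the continuation criteria are met, and sends the reader back to Section 4.4 for them.

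**The concern.** The opening of Section 4.4 makes the list a set of conditions for continuing. Criterion 3 describes a reason for stopping. With no negation in the item or in the opening sentence, it is satisfied only when continuing is no longer justified.

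This is an operative treatment and safety rule. Eligibility to continue has to be documented when the decision is made, and Section 11.6 requires the study to be run exactly as the approved protocol describes. An investigator who does the clinically correct thing therefore departs from the written criterion. Criterion 3 is also the only explicit benefit-risk condition in the list. Section 8.3.1 says the authors know of no reported trial of this combination, so there is good reason to state that condition the right way round.

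**Working it through.** No formula or stated figure bears on this point. The check is to read each criterion against the opening of Section 4.4, apply the list to one patient, and look for a correction elsewhere.

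**Step 1: direction of each criterion.** The opening requires the criteria to be met. Four of the five (1, 2, 4, 5) are worded as absences. One of the five (3) is worded as a presence.

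**Step 2: apply the list.** Take a patient who is clinically well, whose repeat scan at least 4 weeks later is not PD, who meets no other discontinuation criterion, whose ECOG status is stable, and who has no threatened organ or critical site.

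| Criterion | As written | Negation restored |
|---|---|---|
| 1. No confirmed PD, no clinical decline | met | met |
| 2. No other discontinuation criterion | met | met |
| 3. Significant PD, benefit-risk unjustified | **not met** | met |
| 4. No ECOG decline | met | met |
| 5. No threat to vital organs or critical sites | met | met |
| Total | 4 of 5 | 5 of 5 |

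This is the patient the section is meant to keep on treatment.

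**Step 3: compare with the surrounding text.** The closing sentence of Section 4.4 permits treatment when lesions have regressed and PD criteria no longer apply. The Treatment Plan continues until progression is confirmed. Both favour continuing this patient; literal criterion 3 does not. It also sits badly with criterion 1: a patient with clinical signs of significant PD would hardly be described as free of clinical decline, so it is difficult to picture anyone who meets both.

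**Step 4: look for a correction.** Section 4.6 refers back to Section 4.4 without restating criterion 3. Section 4.8 does not restate it. Appendix E lists no change to Section 4.4. The item is a complete phrase with no visible gap or redaction, so nothing suggests that a word was lost in extraction.

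**Step 5: the two cross-references.** Criterion 2 points to a Section 4.4.2 that does not exist; the discontinuation and removal rules are in 4.3.2, 4.3.4 and 4.8. Criterion 1 points to 6.4.2 for PD by RECIST 1.1, but 6.4.2 is a secondary-endpoint statement about immune-related criteria, and 6.2.1 says irRECIST is not used for treatment decisions. The RECIST definition for treatment decisions is in 6.1.7. The repeat-scan window (at least 4 weeks later and within 8) is in footnote 8 of Table 5-1.

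**Step 6: reach into the analysis.** Section 10.3 uses the maximum response before progression. The stage sizes and cut-offs in Section 10.2 do not depend on the continuation rule.

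**The case against.** The best case against is that this is a slip no treating physician would follow. The intended condition is plain from the sentence itself and from its neighbours. The closing sentence of Section 4.4 is not worded as subject to the five criteria, so it can be read as already admitting the patient in the example. Section 4.6 lets the investigator stop treatment for any reason, and Section 4.8 allows withdrawal when continuing is not in the patient's best interest. The documentation requirement does not call for an item-by-item checklist. The right targets for the two references are partly a matter of inference: criterion 1 resembles the confirmation wording in 6.2.1, and 6.1.7 contains no confirmation rule.

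Most of this stands, and it limits the size of the point. It does not remove it. Nothing in the protocol corrects criterion 3, and the section that relies on the list refers back to it. The closing sentence shows what was intended, but it leaves the section disagreeing with itself. On the references, the sponsor knows which sections were meant and should supply them.

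**Conclusion.** The point holds as a drafting error in an operative rule. One of five criteria states the reverse of what was meant, and the list's only explicit benefit-risk check is inverted. The impact is minor.

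Two stronger readings are tempting and the documents do not support them:

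- A reader might infer that the protocol directs treatment of patients who are deteriorating. It does not. Such a patient fails criterion 1 through clinical decline, and criterion 4 or 5 if performance status has fallen or a vital organ or critical site is threatened. Sections 4.3.2, 4.6 and 4.8 provide further grounds to stop.
- A reader might infer that the primary result is at risk. Response is counted before progression, so the objective response rate is unaffected, as are the error rates and sample size.

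The note to criterion 1, which allows treatment after confirmed PD at the clinician's discretion, is a stated exception and is not in question. The two wrong references are clerical, since the rules they should point to can be found. The conclusion assumes that the listed criteria must all be met, as the opening of Section 4.4 says, and that progression in Section 10.3 means RECIST 1.1 progression.

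**What to change.** Begin criterion 3 of Section 4.4 with 'Absence of', change 'such as' to 'such that', and leave the rest of the item as it stands.

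As clean-up in the same amendment, the sponsor should confirm and correct the two references: in criterion 2, replace 4.4.2 with 4.3.2, 4.3.4 and 4.8; in criterion 1, replace 6.4.2 with 6.1.7 for the definition of PD and footnote 8 of Table 5-1 for the repeat-scan window.

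The cost is a wording amendment. Nothing changes in the sample size, the error rates or the primary analysis.
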